9.3 Exclusion Criteria

- Patients with asthma or COPD not on inhaled therapy for maintenance treatment
- Patients younger than 18y

- Patients unable to give their informed consent due to mental or physical disability
- Patients who don't speak French or Dutch

9.4 Contraception/Pregnancy Avoidance NA

10 Screening and Randomization

10.1 Screening and Enrollment

Patients who gave their informed consent will be screened for eligibility by an investigator.

10.2 Randomization NA

10.3 Blinding Procedures NA

11 Interventions/Treatment

11.1 Treatments Administered

The intervention consists of physiological measurements. No treatment, drug or product will be administered. No device will be tested. The In-check-dial-device and placebo pMDI are merely tools to perform the physiological measurements.

11.2 Product Characteristics NA

11.3 Randomization and Stratification NA

11.4 Direction of Administration NA

11.5 Dosing Regimen NA

11.5.1 Dose Modifications and Dose Delay

11.5.2 Treatment Interruption and Treatment Discontinuation

11.6 Treatment Compliance NA

11.7 Study Drug or Medical Device Accountability NA

11.8 Storage, Packaging and Labeling NA

11.9 Blinding NA

11.10 Prior and Concomitant Medication NA

11.11 Non-Drug Therapies NA

11.12 Prohibited Medication NA

11.13 Prohibited Procedures NA

11.14 Other Interactions NA

11.15 Study Disposal and Destruction NA

11.16 Known Undesirable Effects of Study Drug NA

12 Study Assessments and Procedures

Please see section 6.2: study activities

12.1 Study Assessments:

12.1.1 *Screening*
cfr supra (6.2 and 10.1)

12.1.2 *Baseline:* NA

12.1.3 *Run-In:* NA

12.1.4 *Treatment Period:* NA

12.1.5 *Follow-Up*

12.1.6 *End of Study*

The study will end when the anticipated number of participants will be reached.

12.1.7 *Re-screening* NA

12.1.8 *Early Termination* NA

12.1.9 *Unscheduled Visits* NA

NA= not applicable for this cross-sectional study

12.2 Assessment Types

This study will assess physiological data (ability to perform a voluntary inhalation, PIF, and actuation-inhalation coordination with a pMDI). Cfr supra.

- 12.2.1 *Efficacy Assessment* NA
- 12.2.2 *Safety and Tolerability Assessments* NA
- 12.2.3 *Physical Examination* NA
- 12.2.4 *Vital Signs, Height, Weight...*
 - The height and weight of patients will be collected from the patient file.
- 12.2.5 *ECG....* NA
- 12.2.6 *Laboratory Evaluation* NA
 - 12.2.6.1 *Clinical Chemistry*
 - 12.2.6.2 *Hematology*
 - 12.2.6.3 *Urine Analysis*
 - 12.2.6.4 *Pharmacokinetics....*

13 Safety Monitoring and Reporting

Patient safety during the assessments is monitored by the investigators. In the highly unlikely event of an adverse event (AE) or severe adverse event (SAE), this will be reported in the CRF and the treating physician will immediately be notified by the investigator.

The assessments of a deep inhalation, PIF maneuvers over a resistance and the use of a placebo pMDI do not differ from the maneuvers performed in daily life, when inhaler therapy is used by patients.

- 13.1 *Adverse Events* NA
 - 13.1.1 *Definitions and Reporting*
Reporting in the CRF
 - 13.1.2 *Reporting Period*
Duration of the study for the individual patient
 - 13.1.3 *Laboratories Test Abnormalities:* NA
- 13.2 *Serious Adverse Events*
 - 13.2.1 *Definitions*
 - 13.2.2 *Immediate Reporting*
Immediate reporting in the CRF and to the treating physician by the investigator

13.3 Suspected Unexpected Serious Adverse Events (SUSAR) NA

13.3.1 *Definitions*

13.3.2 *Reporting*

13.4 Other safety data requiring an immediate declaration NA

13.5 Procedures for Handling Special Situations NA

13.5.1 *Pregnancy*

13.5.2 *Overdose Management*

13.6 Annual Safety Report NA

14 Data Collection and Management

14.1 Monitoring

14.1.1 *Composition of data monitoring committee: NA*

14.1.2 *Interim analysis: NA*

14.2 Data Collection

By the investigator (from medical records and study assessments).

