13.3 Suspected Unexpected Serious Adverse Events (SUSAR)	19
13.3.1 Definitions.....	19
13.3.2 Reporting	19
13.4 Other safety data requiring an immediate declaration	19
13.5 Procedures for Handling Special Situations	19
13.5.1 Pregnancy	19
13.5.2 Overdose Management.....	19
13.6 Annual Safety Report	19
14 Data Collection and Management	19
14.1 Monitoring	19
14.1.1 Composition of data monitoring committee.....	19
14.1.2 Interim analysis	19
14.2 Data Collection	19
14.3 Database Management and Quality Control	19
14.4 Statistical Considerations and Data Analysis	19
15 Ethical Considerations.....	20
15.1 Ethical conduct of the study	20
15.1.1 Declaration of Helsinki.....	20
15.1.2 Ethics Committee	20
15.2 Informed Consent	20
15.3 Patient and Study Data Protection	20
15.4 Subject Identification	20
16 Finance and Insurance	20
17 Reporting and Dissemination	21

18	Conflict of Interest Statement.....	21
19	Tables and Figures.....	22
20	References	23

1 Trial Registration/Protocol Summary

Information	
EudraCT number:	
Date of registration:	Application for registration in a clinical trial registry will be done after obtaining approval from the ethics committee
ClinicalTrials.gov:	Please see previous line
Official Title:	Choice of inhalation device in asthma and COPD
Study Phase/Type:	Single center, single visit cross-sectional interventional study without device or investigational product.
Condition:	Asthma and COPD (Chronic Obstructive Pulmonary Disease)
Objectives:	To identify patient/inhalation device mismatch by using objective measurements.
Investigational Product or Medical Device:	NA
Interventions:	The intervention will be a three-step evaluation. Patients will perform a deep voluntary inspiration. This inspiration will be assessed by the investigator. Secondly, the peak inspiratory flow will be measured over 5 different resistances with an In-check Dial device. Subsequently, patients will receive education about good coordination technique, which is necessary for the optimal use of pressured metered dose inhalers (pMDIs). By using a placebo pMDI, the investigator will assess the coordination of the patient. The evaluation of voluntary deep inspiration, PIF's and coordination will be by pass or fail evaluation.

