6.1 Study Schematic

Characteristics of the study	
Informed consent procedure:	
 ▪ Available in Dutch and French ▪ Signature and date written by participant
Inclusion criteria:	
 ▪ COPD patients (GOLD II-IV) ▪ Patients with severe asthma ▪ Patients with asthma aged ≥ 70y ▪ Patients with mild-to moderate asthma aged < 70y
Exclusion criteria:	
 ▪ Patients with asthma or COPD not on inhaled therapy for maintenance treatment ▪ Patients younger than 18y ▪ Patients unable to give their informed consent due to mental or physical disability ▪ Patients who don't speak French or Dutch
Collection of data form patient file:	
 ▪ Choice of inhaler by physician (current inhaled maintenance treatment) ▪ GOLD grade and group (COPD patients) ▪ GINA treatment step (asthma patients) ▪ Smoking status ▪ Height ▪ Weight ▪ Age ▪ FEV₁, FVC, PIF if available ▪ Oral corticosteroid maintenance dose
Study assessments:	
 ▪ Voluntary deep inhalation ▪ Peak inspiratory flows (PIF's) ▪ Coordination (through a placebo pMDI)
Reporting to treating physician in case of patient/device mismatch	
 ▪ To avoid prescription of inappropriate inhaler

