6.2 Study Activities

The study will take place in the respiratory outpatient clinic. Patients will be invited to participate in the study after the consultation with the pulmonologist. All pulmonologists have a flowchart regarding the optimal choice of inhaler at their disposition.

Patients will be provided sufficient time to read the informed consent file and to ask questions about the study. After giving their informed consent they will be screened for eligibility by an

investigator. Demographic data and characteristics will be retrieved from the medical record (EMD) of study participants.

The intervention will consist of three different steps.

First, the patient will perform a deep voluntary inspiration. The patient's ability to perform this inspiration will be assessed and scored by the investigator.

Secondly, the peak inspiratory flows (PIF) will be measured with an In-check Dial device over 5 different resistances.

The minimal and optimal peak inspiratory flow rates (PIFRs) differ by device. A minimum flow of 30 L/min is required for most DPI's. The optimal flow varies from 30 L/min to 35, 45, 50, 60 or 65 L/min. (10)

Due to the fact that there is still discussion about the effectiveness of PIF's going from 30 to 60 L/min, an arbitrary cut-off value will be set at 45 L/min. This cut-off value for sufficient PIF will be measured over a moderate resistance to distinguish subtherapeutic from therapeutic levels. (11) If the patient reaches a PIF lower than 45 L/min, the patient will be asked to make a second attempt.

Subsequently, the patient will receive education about the correct coordination, which is necessary in the use of dose inhalers. The patient will be evaluated for sufficient actuation-inhalation coordination, through a placebo pMDI.

The evaluation of the voluntary deep inspiration, PIF and coordination will be by pass or fail evaluation. Subsequently, the fitness of a patient to use any of the three inhaler classes will be determined by using a diagram designed by a Belgian expert group (unpublished to date; courtesy of [name], ULiège).

If a mismatch between prescribed inhaler and suitable inhaler types is found, the treating physician of the patient will be informed. By doing so, we wish to avoid patients receiving prescriptions for inhalers that they cannot use properly.

7 Study Objectives and Endpoints

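### Nothing requires the investigator-judged tests to be scored before the prescribed inhaler class is known, so the primary mismatch prevalence is open to differential scoring

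*Protocol*

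**What the plan says.** Mismatch has two sides, and both come from the same role. Section 14.2 describes data collection as "By the investigator (from medical records and study assessments"). One side is the prescribed inhaler, which section 6.1 lists among the items taken from the patient file: "Choice of inhaler by physician (current inhaled maintenance treatment"). The other side is the set of three tests in section 6.2, which a diagram converts into the inhaler classes the patient is fit to use.

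On scoring, section 6.2 says of deep inspiration: "The patient's ability to perform this inspiration will be assessed and scored by the investigator". For coordination, the protocol summary (section 1) says: "By using a placebo pMDI, the investigator will assess the coordination of the patient". All three tests are reduced to two categories: "The evaluation of the voluntary deep inspiration, PIF and coordination will be by pass or fail evaluation". Only peak inspiratory flow has a number attached, 45 L/min over a moderate resistance, with a second attempt if the first falls short.

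On masking, the protocol has "10.3 Blinding Procedures NA", and section 11.9 repeats NA. On sequence, section 6.2 mentions eligibility screening and then "Demographic data and characteristics will be retrieved from the medical record (EMD) of study participants", and turns to the tests after that. The retrieval sentence carries no time marker. Section 7.1 and the endpoint in section 1 describe the assessments as objective, and section 1 contrasts them with a physician choice that it calls mainly subjective.

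**The concern.** The study asks whether test-based suitability agrees with what the physician prescribed. That comparison is informative only if the test side is obtained independently of the prescription. Two of the three tests rest on a human judgement for which the text gives no instrument, threshold, checklist or second rater. An assessor who knows the patient uses, say, a pMDI may look harder for a coordination fault, or may be more lenient. Either would move borderline results in a way that depends on the comparator.

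The prevalence of mismatch is the primary objective, and the fail rates per test are secondary, so both would be affected. Scoring error of this kind is not reduced by recruiting more patients. Section 14.3 also leaves quality control to the promotor and investigators of the same division, so no independent later check is described.

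**Working it through.** The protocol gives no expected mismatch rate, power or sample-size calculation, so there is no stated figure to reproduce. The check is a reading of the text followed by an illustration of scale.

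**Text**

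1. Who collects: section 14.2 gives records and assessments to one role. Section 3 lists several investigators and section 10.1 speaks of an investigator, so the same person may do both tasks for a patient but need not.
2. What is collected from the file: section 6.1 includes the prescribed inhaler, GOLD grade and group, and GINA treatment step.
3. When: in section 6.2 the ordering words begin with the three tests. Screening and retrieval are described before them, but no order between file look-up and scoring is stated.
4. Safeguard: none is stated in sections 6.2, 10.3, 11.9 or 14.2.
5. Criteria: peak inspiratory flow has one; the other two tests have none in the readable text. The diagram in section 19 is not shown and might contain some.

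**Scale**

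Planned N = 40 + 20 + 40 + 40 = 140 (section 1). If k patients have their final mismatch classification flipped in the same direction, the prevalence moves by k/140:

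- k = 7: 7/140 = 5.0 points
- k = 14: 14/140 = 10.0 points
- in the severe asthma group, one flipped patient: 1/20 = 5 points

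These are upper bounds when k counts changed test scores. A changed score alters the classification only if, through the diagram, it alters suitability for the class that patient is prescribed. It adds to the shift only if it goes the same way as the others.

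To set this against sampling error, let p be the true prevalence, Se the chance that a true mismatch is classified as one, and Sp the chance that a true match is classified as one. All three are assumptions.

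- Observed prevalence = p × Se + (1 − p) × (1 − Sp)
- 95% half-width = 1.96 × √(p(1 − p)/140)

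| Assumed p | Half-width (points) | Bias if Sp = 0.90, Se = 1 | Bias if Se = 0.80, Sp = 1 |
|---|---|---|---|
| 10% | 5.0 | +9.0 | −2.0 |
| 20% | 6.6 | +8.0 | −4.0 |
| 30% | 7.6 | +7.0 | −6.0 |
| 40% | 8.1 | +6.0 | −8.0 |
| 50% | 8.3 | +5.0 | −10.0 |

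Example at 30%, Sp = 0.90, Se = 1: 0.30 × 1 + 0.70 × 0.10 = 0.37, a rise of 7.0 points. Errors in both directions can cancel: at p = 50% with Se = Sp = 0.90, 0.50 × 0.90 + 0.50 × 0.10 = 0.50, so the net bias is zero. Under these assumptions the bias may be as large as the sampling error or may vanish. The documents do not say which case applies.

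**The case against.** Several stronger readings are tempting, and the documents do not support them.

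- A reader might infer that section 6.2 prescribes opening the record before the tests. It describes retrieval earlier in the text but fixes no order. The protocol is silent; it does not require unmasked scoring.
- A reader might infer that one individual does both tasks. The text names a role and lists several investigators.
- A reader might infer that the two judged tests have no criteria at all. The diagram is not shown, so this can be said only of the readable text.
- A reader might infer that every shifted score moves the prevalence. A different coordination result, for instance, need not change suitability for a patient prescribed a dry powder inhaler.
- A reader might take NA for blinding as a refusal of assessor masking. In a study with no treatment it may mean only that there was no treatment to blind. It shows that nothing was planned.

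There is also a practical objection. The exclusion in section 9.3 needs only a yes or no on inhaled maintenance therapy, but section 9.2 also requires COPD grade or asthma severity. Screening may therefore open a record that shows the product. Fixing the CRF order does not erase what the assessor has seen, and age and diagnosis cannot be hidden, so part of any bias between subgroups would remain. This stands, and it limits what the remedy can achieve.

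Finally, section 14.4 calls the study purely explorative, and peak inspiratory flow is read from an instrument. Both points lower the stakes. They do not remove the gap, because the prevalence is still the primary result and two of its three inputs are judged. The order of scoring and look-up is a matter of study conduct, so it belongs in the protocol.

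**Conclusion.** The point holds as an unprotected comparison, not as a demonstrated bias. One role handles both the prescribed inhaler and the tests, two tests are judged without a criterion in the readable text, and nothing requires scoring before the prescribed class is known. Differential scoring of borderline manoeuvres is therefore possible and could bias the primary prevalence; its direction and size are unknown. The 5-point figure for 7 of 140 patients rests on an assumed count, on every flip going the same way, and on each flip changing the final classification. The change is a cheap improvement, and my confidence in the point is moderate.

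**What to change.** Amend sections 6.2, 10.3 and 14.2 to state that:

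- screening records inhaled maintenance therapy only as yes or no;
- the three pass/fail results are entered and signed in the CRF before the prescribed device class is looked up or asked about;
- GINA step and the other file data are extracted after scoring where possible;
- mismatch is derived after that.

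Add a CRF tick-box for whether the assessor already knew the device class when scoring, so that the extent of unmasking can be reported. In sections 1 and 7.1, describe deep inspiration and coordination as investigator-rated and reserve the term objective for peak inspiratory flow.

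The cost is protocol wording, CRF page order and one extra CRF item, with no extra staff or procedure. Masking will be partial: the screening record or the patient may reveal the device, and age and diagnosis remain visible.

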14.3 Database Management and Quality Control

The promotor and investigators from UZ Brussel's respiratory division assume database management and quality control.

14.4 Statistical Considerations and Data Analysis

The promotor and investigators from UZ Brussel's respiratory division will perform the statistical analysis, with the help of VUB statistician [name].

The statistical plan was discussed during a meeting with professor [name] (see below).

Sample size calculation

This is a purely explorative study, since there is no a priori hypothesis to be confirmed. Hence, no formal sample size calculation is possible.

The findings of this study could later on be confirmed and assessed more extensively in larger dedicated studies.

For this study however, it is important that the patient groups be stratified according to their occurrence in society. We believe this will be the case when the in-and exclusion criteria for this study will be applied.

Statistical analysis

Descriptive statistics will be used to describe the prevalence of patient/device mismatch for the entire study population.

The comparison of the prevalence of patient/device mismatch between patient subgroups and the comparison of the fail rates for each objective measurement separately between patient subgroups will be done by means of the Chi-square test and will be visualized in cross-tables.

To study correlations between patient characteristics (independent variables) and pass or fail rates for each of the three test criteria (dependent variables), box-plots will be used for continuous variables (for example weight and length), whereas the Chi-square test will be used for categorical variables (for example diagnosis, age expressed in years, GOLD stage and GOLD group).

15 Ethical Considerations

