Endpoints:	To assess if the choice of inhaler device category differs when based on objective assessments, as compared to the choice made by the treating physician (during routine clinical practice), which is primarily based on subjective evaluation.
Study population:	Asthma and COPD patients treated with inhaled medications. Subjects will be recruited in the respiratory outpatient clinic in UZ Brussel after a scheduled consultation with their pulmonologist.
Number of patients:	40 COPD patients (GOLD II-IV); 20 patients with severe asthma, 40 patients with asthma aged ≥ 70 y, 40 patients with mild-to moderate asthma aged < 70 y
Overview of study design:	Single center, single visit cross-sectional interventional study without device or investigational product
Statistical Considerations:	Descriptive analysis will be used to describe the prevalence patient/device mismatch. Multiple regression analysis will be performed to identify patient characteristics associated with inability to use the 3 main classes of inhalation devices respectively. Due to the exploratory nature of this study, no formal power calculation can be performed.
Sponsor:	This study is an academic study and has no sponsor.
Inclusion Criteria:	
 - COPD patients (GOLD II-IV) - Patients with severe asthma - Patients with asthma aged ≥ 70y - Patients with mild-to moderate asthma aged < 70y
Exclusion Criteria:	
 - Patients with asthma or COPD not on inhaled therapy for maintenance treatment - Patients younger than 18y - Patients unable to give their informed consent due to mental or physical disability - Patients who don't speak Dutch or French
Target Date of first enrolment:	To be determined. Probably Q4 2021.

Target sample size:	No target sample size calculation could be performed due to exploratory nature of the study (please see above)
---------------------	--

2 Protocol Version History

Version No.	Release Date	Summary of Changes

3 Sponsor/Coordinating Investigator Information

Coordinating Investigator (promotor): [name]. [name]

Sponsor: NA

Principal Investigator [name]

Co-investigators: [name]. [name], [name] (co-promotor), [name], [name]

Additional co-researchers: NA

Statistician

Laboratory (ies): NA

Pharmacy: NA

Study Coordinator: [name]

Study sites and co-investigators: respiratory outpatient clinic UZ Brussel

4 List of Abbreviations

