9.1 Selection of Study Population

The selection of study population will take place in the respiratory outpatient clinic in UZ Brussel. The patients will be recruited following their consultation with the pulmonologist.

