9.2 Inclusion Criteria

- COPD patients (GOLD II-IV)
- Patients with severe asthma included in the Belgian Severe Asthma registry aged <70
- Patients with asthma of any severity aged ≥ 70 y
- Patients with mild-to moderate asthma aged < 70y

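### Section 14.4 relies on the eligibility criteria to make the patient groups mirror their frequency in society, but the criteria set no proportions, so the overall mismatch prevalence is specific to this sample's composition

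*Protocol*

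**What the plan says.** Under the sample size heading of section 14.4, the protocol says that "it is important that the patient groups be stratified according to their occurrence in society". It then gives the only stated means of getting there: "We believe this will be the case when the in-and exclusion criteria for this study will be applied".

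The criteria in 9.2 and 9.3 describe four groups and some exclusions. One group, for example, is "Patients with severe asthma included in the Belgian Severe Asthma registry aged <70". COPD is limited to GOLD II-IV. On the source of patients, 9.1 says: "The selection of study population will take place in the respiratory outpatient clinic in UZ Brussel".

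The numbers per group appear only in the protocol summary (section 1). That entry begins "40 COPD patients (GOLD II-IV); 20 patients with severe asthma, 40 patients with asthma aged" and continues with the age limit of 70 or over and a further 40 with mild-to-moderate asthma under 70. Section 12.1.6 adds: "The study will end when the anticipated number of participants will be reached".

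The primary objective (7.1) is the prevalence of patient/device mismatch. The analysis in 14.4 reads: "Descriptive statistics will be used to describe the prevalence of patient/device mismatch for the entire study population". Mismatch by subgroup is a secondary objective (7.2), and 14.4 plans a chi-square comparison between subgroups.

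**The concern.** The protocol names a property of the sample that it considers important and names the mechanism that should produce it. Eligibility criteria decide who may enter; they do not decide how many enter from each group. The property therefore has no mechanism behind it.

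What is at stake is the reading of the headline result. A single prevalence pooled over four groups is a weighted average, with the group shares as weights. Someone who takes 14.4 at its word would read that average as reflecting the mix of asthma and COPD patients in society. The design gives no basis for that reading.

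**Working it through.** **1. Do the criteria set proportions?** Sections 9.2 and 9.3 contain definitions by diagnosis, severity, age, registry membership, maintenance therapy, consent capacity and language. None contains a share or a ratio. Two groups are narrower than the disease in society (GOLD II-IV only; registry patients only for severe asthma under 70), and recruitment is at one hospital clinic.

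**2. What does set the mix?** There are two readings of section 1 together with 12.1.6.

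- Counts met per group: 40 + 20 + 40 + 40 = 140. Shares are 40/140 = 28.6% COPD, 20/140 = 14.3% severe asthma, 40/140 = 28.6% asthma aged 70 or over, and 40/140 = 28.6% mild-to-moderate asthma under 70. These hold whatever the criteria say.
- Recruitment stopped on the total: the mix follows who attends the clinic and consents.

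No section ties either to population frequencies.

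**3. Can the protocol's own epidemiology confirm or refute the planned mix?** Section 5.2 gives asthma at a = 4.3% worldwide or 8.4% in the United States, and COPD at c = 9-10% of adults over 40. The share of the population over 40, f, is not given; 0.3 to 0.6 is assumed here. COPD share of asthma plus COPD = c·f / (c·f + a):

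- a = 4.3%: from 0.027/(0.027 + 0.043) = 39% to 0.060/(0.060 + 0.043) = 58%.
- a = 8.4%: from 0.027/(0.027 + 0.084) = 24% to 0.060/(0.060 + 0.084) = 42%.

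The planned 28.6% lies inside the second range and outside the first. The check is rough: the denominators differ, and only GOLD II-IV is eligible. For severe asthma and for asthma at 70 or over the protocol gives no population figure, so the 20/40/40 split within asthma cannot be checked at all.

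**4. How does the mix enter the primary result?** With group rates p1 to p4 and the planned counts met, the overall prevalence is (40·p1 + 20·p2 + 40·p3 + 40·p4)/140. Moving share d from group i to group j changes it by d·(pj − pi). For d = 0.10 and rate gaps of 0, 10, 20 and 30 points, the change is 0, 1, 2 and 3 points. For any mix, the overall value stays between the lowest and highest group rate.

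**5. Illustration.** All rates, and the two alternative mixes, are assumed. Order: COPD, severe asthma, asthma 70 or over, mild-to-moderate under 70.

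| Assumed group rates | Planned 40/20/40/40 | Mix 30/3/12/55% | Mix 50/3/12/35% |
|---|---|---|---|
| 40/30/40/15% | 44/140 = 31.4% | 26.0% | 31.0% |
| 50/40/50/10% | 52/140 = 37.1% | 27.7% | 35.7% |
| 30% in every group | 30.0% | 30.0% | 30.0% |

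The shift can be several points, negligible, or zero, depending on quantities the protocol does not contain.

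**The case against.** The best defence is that little harm is left. The study calls itself purely explorative and expects later confirmation. The analysis text limits the overall figure to the study population, the primary objective makes no claim about society, and subgroup prevalences are already planned; these do not depend on the mix. All of this stands, and it is why the point is minor. It does not rescue the sentence in 14.4, which attributes to the criteria something they cannot do. The exploratory aim explains the remark "No target sample size calculation could be performed due to exploratory nature of the study", but that remark concerns total size and says nothing about how the group split was chosen.

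The wording can also be defended as loose: stratified by occurrence may not mean proportional to it. Proportionality is still the most natural meaning, and the text offers no other.

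Several stronger readings are tempting and are not supported:

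- *The mix is wrong for society.* The documents do not show this. Step 3 leaves open that the COPD share is about right, and the rest cannot be checked.
- *The counts are fixed quotas.* Section 1 labels them as numbers of patients, and 12.1.6 does not say that stopping is per group. Per-group filling is the natural reading, but it is an inference.
- *Mismatch is known to differ by age.* Section 5.4 says poor inhaler use is commonest in older people. That concerns misuse, not mismatch as assessed here, so it gives a reason to doubt equal rates and no proof that they differ.
- *A clinic denominator is unavailable because eligibility is screened after consent.* The order of those steps does not settle whether clinic numbers are counted; the protocol is silent.

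**Conclusion.** The point holds as a minor one. The statement in 14.4 that the criteria will bring the groups into line with society is unsupported: the criteria carry no proportions, and whatever sets the mix (planned counts, or attendance and consent) is not linked to population frequencies. The overall mismatch prevalence is a correct description of the patients studied. A reader might infer that it is biased; that does not follow, because it departs from a prevalence for society only if group rates differ and the mixes differ, and the documents establish neither. What can be said about size is conditional: 1 point for each 10 points of share moved per 10-point gap in group rates, and nothing if rates are equal. The weights 28.6/14.3/28.6/28.6% assume that the planned counts are met group by group.

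**What to change.** In section 14.4:

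- Delete the statement that applying the criteria makes the groups follow their frequency in society.
- State that the mix follows the planned group counts, and confirm that these are to be filled per group, since 12.1.6 leaves this open.
- Describe the overall prevalence as specific to this sample's composition.
- Present the group-specific prevalences already planned in 7.2 beside it, as the figures to interpret.

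This is wording and presentation only; the planned counts and the data collected stay as they are. The price is a narrower claim for the headline figure. If the investigators want an overall figure that generalises, they would need to standardise it to a stated reference mix with a documented source, which the protocol does not now contain. That step is optional.
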